## 8.5 Safety

Safety data including AEs, vital signs, laboratory data, ECG, ophthalmologic assessment findings, and other physical exam findings will be summarized for the safety population. AEs will be tabulated by system organ class (SOC), preferred term, severity, and relationship to treatments. The tabulation of laboratory parameters will include the normal ranges for each parameter. AE terms will be coded using the Medical Dictionary for Drug Regulatory Activities, version 22.1 or higher. AEs will be summarized by SOC, preferred term, severity, and relationship to treatment. SAEs, deaths, and AEs leading to APR-548 dose modifications including interruptions, reductions, and early discontinuation of study treatment will be summarized. Laboratory parameters will be summarized by maximum NCI-CTCAE version 5.0 severity grade and also by change from pre-treatment to scheduled time points using descriptive statistics. Laboratory parameter listings will include the normal ranges for each parameter. Each value will be classified as falling above, below, or within the normal range.

AEs are to be collected from the time of first dose of APR-548 and SAEs are to be collected from the time of signing informed consent, throughout study enrollment, and up to 30 days after last dose of APR-548 or azacitidine, whichever is later. Data summaries will include only TEAEs, defined as events occurring at the first administration of APR-548 up to and including 30 days after last dose of study treatment.

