	
cycle of APR-548 and who have at least one post-treatment clinical response assessment. The EE population will be the secondary analysis population for efficacy.
 
PK population: Subjects will be evaluable for PK if at least one sample for PK evaluation has been obtained.
 
Safety Analyses
 
Safety data including AEs, vital signs, laboratory data, electrocardiogram (ECG), ophthalmologic assessment findings, and other physical exam findings will be tabulated for the safety population. AEs will be tabulated by System Organ Class (SOC), preferred term, severity, and relationship to treatments. The tabulation of laboratory parameters will include the normal ranges for each parameter. Each value will be classified as falling above, below, or within the normal range. Laboratory parameters will also be tabulated by maximum NCI-CTCAE v5.0 severity grade.
 
Efficacy Analyses
 
CR rate will be summarized for the safety and EE subjects as the proportion (%) of subjects with CR. In addition to presenting the CR rate, its associated exact 95% confidence intervals (CI) for each treatment arm will also be presented.
 
DOR is defined as the time from the date when criteria for response are met to the date of relapse/PD or death due to any cause, whichever occurs first. Subjects alive with no relapse/PD will have their DOR censored at the date of the last clinical assessment. The DOOR will be summarized in each treatment arm by providing the median DOR together with associated 95% CI, using Kaplan-Meier methodology.
 
Overall response will be summarized in number (%) of subjects in each category of responses (CR, PR, marrow complete response [mCR] with HI, mCR without HI, HI). ORR will be analyzed by using the similar method as primary endpoint CR. DOR, as defined above, will also be evaluated in regard to ORR. Time to AML is calculated from first day of study treatment to first onset of AML. Kaplan-Meier methodology will be utilized. Rate of AML transformation will be analyzed by using the similar method as primary endpoint CR.
 
Survival data are collected at treatment and follow-up periods. Subjects will be followed until death or withdrawal of consent from the study, whichever occurs first.
 
OS is defined as the number of days from the first day of treatment to the date of death due to any cause. Kaplan-Meier methodology will be utilized.
 
RFS is defined as the time from the date of randomization to disease relapse or death, whichever occurs first. If neither event occurs, RFS will be censored at the date of the last clinical assessment. Kaplan-Meier methodology will be utilized.
 
Time to AML, OS and RFS will be analyzed using the similar methods as DOR.
 
Transition rate to HSCT will be analyzed using the similar methods as CR.

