## 2.0 BACKGROUND INFORMATION

### 2.1 Disease Background

Myelodysplastic syndromes (MDS) are a heterogeneous group of neoplasms arising from a clonal hematopoietic precursor. MDS is characterized clinically by cytopenia and a tendency to transform to acute myeloid leukemia (AML). Prognostic scoring systems have been developed to help stratify patients based on predicted survival and progression to AML. In practice, treatment decisions are made by grouping patients with MDS into lower and higher risk subgroups as defined by clinical prognostic scoring systems. Specifically, the International Prognostic Scoring System (IPSS) and its more modern version, the revised-IPSS (IPSS-R), represent the most widely used clinical prognostic tools. Those patients that fall in the higher risk group have an expected survival of less than 12 months if left untreated and progress to AML greater than 30% of the time.

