	2 nd occurrence	
 
• Interrupt APR-548 dosing and monitor subject; treat promptly.
 
• Reduce APR-548 by 1 dose level if the toxicity resolves to Grade ≤1 or baseline within 72 hours of onset.
 
• If toxicity does not resolve to Grade ≤1 despite maximal medical intervention(s) within 72 hours of onset, then consult with study Medical Monitor before resuming or discontinuing APR-548.
 
• If unable to reduce APR-548 dose, discuss with study Medical Monitor before resuming or discontinuing treatment.
 
• Prior to subsequent doses of APR-548, reassess prophylactic supportive therapy regimen and adjust as clinically indicated.
 

	3 rd occurrence	
 
• Interrupt APR-548 dosing and monitor subject; treat promptly.
 
• Consult with study Medical Monitor before resuming or discontinuing APR-548.
 

Grade 4	
 
• Interrupt APR-548 dosing and monitor subject; treat promptly.
 
• Consult with study Medical Monitor before resuming or discontinuing APR-548.
 
	

\* Refer to Section [5.3.5](#) for details on supportive management guidelines specific to nausea, vomiting, and/or diarrhea.

**Table 6. Dose management guidelines for APR-548 and azacitidine for worsening neutropenia from baseline with or without fever**

Toxicity	Occurrence	APR-548	Azacitidine
Grade 3 or 4 neutropenic fever or Worsening neutropenia from baseline to Grade 4 without fever	1 st occurrence	
 
• Interrupt dosing and monitor subject; treat promptly.
 
• Resume at current dose level if neutropenia and fever (if present) resolve to baseline within 7 days after onset.
 
• If toxicity does not resolve to baseline despite maximal medical intervention(s) within 7 days of onset, then reduce APR-548 by 1 dose level once the toxicity resolves to baseline.
 
• If unable to reduce APR-548 dose, discuss with study Medical Monitor before resuming or
 
	Follow dose modification guidelines per USPI  .

		
discontinuing treatment.
 
 
Initiate or reassess prophylaxis measures. Refer to Sections 5.3.3 and 5.3.4 for supportive management guidelines specific to infection prophylaxis and neutropenia, respectively.
 
	

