## 7.1.2 Reporting of Adverse Events

### 7.1.2.1 Adverse Events

An AE is any untoward medical occurrence in a subject administered a pharmaceutical product that does not necessarily have a causal relationship with the treatment. An AE can be any unfavorable and unintended sign (including a laboratory finding), symptom or disease temporally associated with the use of a medicinal (investigational) product, whether or not related to the medicinal (investigational) product.

The AE reporting period starts at the time of study treatment initiation. At each evaluation, subjects should be interviewed in a non-directed manner to elicit potential adverse reactions from the subject. The occurrence of an AE will be based on changes in the subject's physical examination, laboratory results, and/or signs and symptoms.

For the time period from signing of informed consent up to receipt of the first dose of APR-548, non-serious events should be recorded as medical history on the appropriate eCRF page within the clinical database. SAEs that occur during the screening period are required to be reported and should include an assessment on whether the SAE was related to a protocol-defined procedure or activity.

All AEs (except laboratory abnormalities that are assessed as not clinically significant by the investigator, or examining ophthalmologist as applicable), regardless of causal relationship, are to be recorded in the eCRF and source documentation. The investigator must determine the intensity of any AEs according to the NCI-CTCAE version 5.0 and their causal relationship to each study medication administered that has been administered to the subject at the time of event onset. Those AEs not covered by these criteria will be graded as follows:

1. Mild: Discomfort noticed, but no disruption of normal daily activity. Prescription drug not ordinarily needed for relief of symptom but may be given because of personality of subject.
2. Moderate: Discomfort sufficient to reduce or affect normal daily activity. Subject is able to continue in study; treatment for symptom may be needed.
3. Severe: Incapacitating, severe discomfort with inability to work or to perform normal daily activity. Severity may cause cessation of treatment with test drug; treatment for symptom may be given and/or subject hospitalized.

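### The maximum-grade haematology table does not separate cytopenia present at entry from new or worsened Grade 3-4 cytopenia, and no baseline-to-worst-grade shift table is planned

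*Combined protocol and SAP*

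**What the plan says.** Section 8.5 plans three kinds of laboratory output besides listings.

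- Graded and quantitative: "Laboratory parameters will be summarized by maximum NCI-CTCAE version 5.0 severity grade and also by change from pre-treatment to scheduled time points", using descriptive statistics.
- Normal range: "Each value will be classified as falling above, below, or within the normal range".
- The synopsis, under Safety Analyses, has the normal-range classification and this: "Laboratory parameters will also be tabulated by maximum NCI-CTCAE v5.0 severity grade". It does not mention the change summary.

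Section 8.0 adds that continuous variables are shown with n, mean, median, standard deviation, minimum and maximum, and that data are presented by dose level.

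Neither Section 8.5 nor the synopsis plans a cross-tabulation of baseline grade against worst post-baseline grade or a count of subjects whose grade worsened. Neither states that the maximum grade is taken over post-baseline values only. The term pre-treatment is not defined.

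On the population, Section 2.1 says: "MDS is characterized clinically by cytopenia and a tendency to transform". Inclusion criterion 3 in Section 4.7 limits only creatinine clearance, bilirubin and ALT/AST. Exclusion criterion 15 lets the investigator exclude for a laboratory abnormality but gives no blood-count value.

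**The concern.** A maximum-grade table answers the question of how low a subject's counts went. In most populations that is close to the question of what treatment did, because subjects start near normal. Here they need not. A subject who enters with Grade 4 neutropenia and stays there appears as maximum Grade 4, just like a subject who enters normal and falls to Grade 4 after APR-548.

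Myelosuppression is an obvious laboratory harm to look for when a new drug is added to azacitidine. Cohorts have 3 to 6 subjects, so a chance difference in entry counts between dose levels can look like a dose effect, or hide one. The same subjects also pass from monotherapy to combination, sometimes at a different APR-548 dose (Section 4.1). A single maximum per subject would mix the two periods.

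The protocol refers to baseline elsewhere. Table 2 is limited to new-onset haematologic toxicity, and Table 6 covers "worsening neutropenia from baseline with or without fever". The analysis section does not carry that reference into its grade table.

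**Working it through.** The plan gives no figure for this point, so there is none to reproduce. The check has three steps.

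**1. Can subjects enter with severe cytopenia?** Yes. No eligibility criterion sets a minimum count. Appendix VI lists cytopenia in the MDS categories. Appendix V has a platelet-response rule for subjects starting below 20 × 10⁹/L, so very low entry counts are foreseen. How often they occur is not stated.

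**2. What does the maximum-grade table show?** Let b be the share entering with Grade 3-4 cytopenia that persists on treatment, and w the share of the others who newly reach Grade 3-4. Both are assumptions.

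- Maximum-grade table: b + (1 − b)w
- Newly Grade 3-4, as a shift table would show: (1 − b)w
- The difference is b.

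| b | w | Maximum-grade table | Newly Grade 3-4 |
|---|---|---|---|
| 0% | 10% | 10% | 10% |
| 20% | 10% | 28% | 8% |
| 40% | 10% | 46% | 6% |
| 60% | 10% | 64% | 4% |
| 0% | 30% | 30% | 30% |
| 20% | 30% | 44% | 24% |
| 40% | 30% | 58% | 18% |
| 60% | 30% | 72% | 12% |

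For one cohort of 6 with no drug effect (w = 0), the expected number shown as Grade 3-4 is 6b, and P(at least 2 of 6) = 1 − (1 − b)⁶ − 6b(1 − b)⁵:

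- b = 20%: 1.2 subjects; 1 − 0.262 − 0.393 = 0.34
- b = 30%: 1.8 subjects; 1 − 0.118 − 0.303 = 0.58
- b = 50%: 3.0 subjects; 1 − 0.016 − 0.094 = 0.89

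The threshold of two only illustrates scale; no rule in the protocol counts subjects in this table.

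**3. Do the other outputs recover the information?** In part.

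- *Change summary.* Take an invented cohort with baseline neutrophils 0.4, 0.4, 0.4, 2.5, 2.5, 2.5 and later values 1.1, 1.1, 1.1, 2.5, 2.5, 0.4. The changes are +0.7 three times, 0 twice and −2.1 once. The mean is (2.1 − 2.1)/6 = 0.0, although one subject has newly fallen below an assumed cut-off of 0.5. The minimum of −2.1, required by Section 8.0, does reveal a large fall. It does not give the starting or ending grade, or how many subjects crossed a grade.
- *Timing.* The visit lists in Sections 6.4 and 6.5 put haematology on Days 1, 8 and 21 of the run-in and Days 1, 8 and 15 of Cycle 1. On those lists the gap from Day 8 to Day 21 is 13 days, and from Cycle 1 Day 15 to the next cycle's Day 1 is 14 days. Any further days marked in Table 12 would shorten these gaps. A nadir found at an unscheduled test is outside the change summary.
- *Adverse-event tables.* Before the first dose, "non-serious events should be recorded as medical history on the appropriate eCRF page", which keeps many entry conditions out of the AE tables. But the TEAE definition ("Data summaries will include only TEAEs, defined as events occurring at the first administration of APR-548") has no worsening-from-baseline clause, and Section 7.1.2.1 exempts laboratory abnormalities judged not clinically significant from AE recording. These tables cannot stand in for a laboratory shift table.

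**The case against.** The strongest reply is that the plan does use baseline. The sentence that sets up the maximum-grade table also plans change from pre-treatment. With 3 to 6 subjects per cohort, the minimum and maximum expose one subject's worst fall at each visit, and laboratory listings are planned. The maximum grade is not limited to scheduled visits, so it can capture unscheduled nadirs. This stands. A reader might infer that worsening cannot be seen at all; the documents do not support that. What is missing is the link between a subject's starting grade and worst grade, and a count of those who worsened.

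Three other stronger readings also fail.

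- *That all laboratory toxicity is affected.* Table 9 expresses creatinine grades as multiples of baseline, and Table 10 does so for AST/ALT when baseline is abnormal. The problem is mainly haematology.
- *That dose decisions are distorted.* The myelosuppression DLTs in Section 5.1.3 require absence of disease, and Tables 2 and 6 refer to new onset or worsening. No escalation or RP2D rule uses the laboratory table.
- *That one pre-treatment baseline is applied throughout.* Section 8.5 leaves the term undefined, and combination visits can be told apart from run-in visits by time point. The defect is the missing definition.

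It is also fair to say that the baseline shares are assumed and that some entry cytopenias may improve on treatment. That limits the size of the problem and leaves the mechanism intact.

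**Conclusion.** The point holds as a reporting gap in haematology. Followed as written, Section 8.5 and the synopsis give a maximum-grade table by dose level in which pre-existing and new or worsened Grade 3-4 cytopenia cannot be told apart. The change summary and listings only partly make up for this.

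The excess in the table equals the share of subjects with persisting entry cytopenia. Over an assumed range of 20% to 50%, that is 1.2 to 3.0 of 6 subjects. The share is not in the documents, and the counts also assume that the cytopenia is still present on treatment. Sample size, DLT assessment, dose management and escalation are unaffected. The change is worth making because it bears on how myelosuppression is read by dose.

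**What to change.** Keep the maximum-grade table. In Section 8.5, add for haematology:

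- Shift tables of baseline grade against worst post-baseline grade, using scheduled and unscheduled values, by dose level.
- Separate tables for the monotherapy run-in (baseline: last value before the first APR-548 dose) and the combination (baseline: Cycle 1 Day 1). Also show the combination table against the original pre-treatment baseline, so that cumulative worsening is not lost when the baseline is reset.
- The number worsening by at least one grade, and the number newly reaching Grade 3-4 with its denominator (those below that level at baseline).

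Define pre-treatment, and bring the synopsis into line with Section 8.5, including the change summary it now omits.

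The cost is table programming and more rows, with no added data collection. At-risk denominators will be small: if half of a cohort of 6 entered at Grade 3-4, 6 × 0.5 = 3 subjects would remain. The denominator must therefore always be shown.

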#### **4.1.1 Treatment Duration**

Subjects may continue treatment with APR-548 and azacitidine until disease progression, development of other unacceptable toxicity, confirmed pregnancy, HSCT, death, withdrawal of consent, or study termination, whichever occurs first. Subjects who experience disease progression per the applicable response criteria who are, in the opinion of the investigator, benefiting from treatment, may be allowed to continue on study drug with approval of the Medical Monitor.

Following discontinuation of study drug, subjects are to attend a follow-up visit 28 days after the last dose of study drug for final assessments. When study drug is withheld from a subject in order to resolve a toxicity and the subject does not subsequently restart treatment, end of treatment is defined as the date when the study drug was first held. Subjects should proceed with end of treatment assessments, safety, and survival follow-up. If the decision to not restart study treatment comes outside of the 28-day safety follow-up window, the subject should have an End of Treatment visit and proceed with survival follow-up.

Subjects who achieve an adequate response to treatment with APR-548 and meet other criteria required to undergo HSCT may proceed to HSCT after discontinuation of APR-548. If a subject proceeds to HSCT, evaluation of the extent of disease, response to treatment, and any new antineoplastic therapies will be collected at least monthly as long as the subject remains in remission and assessed as part of the study until relapse, death, withdrawal of

consent, loss to follow-up, or end of study, whichever comes first. If a subject discontinues APR-548 to undergo HSCT, but is then deemed ineligible for HSCT, the subject may restart APR-548 with Medical Monitor approval.

All subjects that enter survival follow-up will be contacted every two months for assessment of survival status and new antineoplastic therapies. Please see Section [6.9](#) for details on long-term follow-up.

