**Table 12. Schedule of assessments**

Assessments	Screening a	Safety Run-In (APR-548 Monotherapy) b										APR-548 + Azacitidine Combination												End of treatment x	Long-term follow-up y
												Cycle 1 (Safety Run-In)						Cycle 2				Cycles 3+			
		D1	D2	D3	D4	D5	D8	D15	D21	D28	D1	D2 - 7	D8	D15	D22	D1 c	D2 - 7	D8	D15	D1 d	D2 - 7	D15 e			
Informed consent	x																								
Mutant TP53 confirmation f	x																								
Medical history g	x																								
Physical examination h	x	x							x	x	x					x	x	x			x			x	
Vital signs h	x	x	x	x	x				x	x	x	x	x	x	x	x	x	x	x	x	x	x	x	x	
Height i	x																								
Weight	x	x							x	x	x					x	x	x			x			x	
ECOG performance status	x	x						x	x	x	x					x	x	x			x			x	
APR-548 j		x	x	x	x						x j	x				x j	x			x	x				
Azacitidine k											x	x				x	x			x	x				
Disease assessment l	x							x												x				x	
Hematology m	x	x					x		x	x	x		x	x	x	x	x	x	x	x	x	x	x	x	
Serum chemistry n	x	x					x		x	x	x		x	x	x	x	x	x	x	x	x	x	x	x	
Creatinine clearance o	x	x				x		x	x	x	x		x	x	x	x	x	x	x	x	x	x	x	x	
Coagulation profile p	x								x				x			x									
Pregnancy test q	x								x						x				x				x	x	
ECG r	x	x	x		x	x					x	x				x				x			x	x	
APR-548 PK sample s	x	x		x	x						x	x				x				x					
Azacitidine PK sample s											x	x													
PBMC/BMMC sample collection t	x					x													x			x			
Blood sample for PD markers u		x	x		x	x					x	x													
Bone marrow biopsy (optional)					x																				
Ophthalmological evaluation v	x						x		x				x	x				x	x	x	x v	x			
Clinical safety assessment w		Starting at the time of study treatment initiation through 30 days after last dose																							
Concomitant medications		Reviewed throughout study																							
Transfusion log		From 8 weeks prior to enrollment to end of treatment/off treatment																							
Survival																								x	

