- t. Peripheral blood/bone marrow (or both; whichever sample is collected for disease assessment) mononuclear cells collection for exploratory biomarker testing. Disease assessment on approximately Day 15 during the monotherapy safety-run in is optional.
- u. Blood sample for PD markers, collected pre-dose, 8 hours post dose, and 24 hours post dose on Day 1 and 4 of the safety run-in and Cycle 1. The 24 h post-dose timepoints correspond to pre-dose Day 2 and Day 5, respectively
- v. Please consult Section [7.6](#) for the schedule of ophthalmological evaluation.
- w. AE description, grade, start date, resolution date, outcome, and relationship to study treatment should be documented. For the time period from signing of informed consent up to receipt of the first dose of APR-548, non-serious events should be recorded as medical history on the appropriate eCRF page within the clinical database. SAE(s) that occur during the screening period are required to be reported and should include an assessment on whether the SAE was related to a protocol-defined procedure or activity.
- x. Visit conducted at 28 days after study treatment discontinuation. A window of  $\pm$ 14 days is allowable for End of Treatment ophthalmological evaluation.
- y. Long-term follow-up can be done remotely (e.g., via telephone, via local practitioner or via review of medical records). All subjects who undergo HSCT following discontinuation of APR-548 are to be followed after the last dose until relapse or end of study. Subjects who respond and discontinue study treatment for reasons other than disease relapse should continue to have response assessments, and survival should be collected every 2 months until disease relapse, withdrawal of consent for study participation, or death, whichever occurs first. After disease relapse, data for survival should be collected every 6 months until death or withdrawal of consent for study participation. If a subject proceeds to HSCT, evaluation of the extent of disease, response to treatment, and any new antineoplastic therapies will be collected at least monthly as long as the subject remains in remission and assessed as part of the study until relapse, death, withdrawal

of consent, lost to follow-up, or end of study, whichever comes first. If a subject is removed from the study due to unacceptable AEs, the event(s) will be followed until resolution or stabilization of the AE.

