## 6.8 End of Treatment Visit

This visit should take place within 28 days of the last dose of study treatment, if treatment is stopped early for any reasons.

- Physical examination
- Weight

- Vital signs
- ECOG performance status ([Appendix II](#))
- Hematology, including complete blood count with white blood cell differential
- Serum chemistry, including sodium, potassium, chloride, magnesium, CO2, BUN, creatinine, glucose, calcium, albumin, total protein, total bilirubin, AST, ALT, alkaline phosphatase
- Creatinine clearance (Cockcroft-Gault method; [Appendix I](#))
- Disease assessment per IWG 2006 criteria ([Appendix V](#))
- Blood and bone marrow for exploratory biomarker sample testing
- Ophthalmologic evaluation per [Table 16](#)
- ECG: standard 12-lead ECG with subject in a semi-recumbent position, per [Table 15](#)
- Serum or urine βhCG
- Clinical safety assessment
- Concomitant medications review
- Transfusion log

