4. Life-Threatening: Symptom(s) place the subject at immediate risk of death from the reaction as it occurred; it does not include a reaction that, had it occurred in a more serious form, might have caused death.
5. Fatal: Event caused the death of the subject.

AEs will be followed until resolution or stabilization while the subject remains on-study. Once the subject is removed from study, events thought to be related to the study medication will

be followed until resolution or stabilization, unless, in the investigator's opinion the event is unlikely to resolve due to the subject's underlying disease, or until the subject starts a new treatment regimen or the subject is lost to follow-up.

The end of the AE and SAE reporting period is 30 days after last dose of study treatment, unless the subject has withdrawn consent for study participation or started new therapy for underlying disease. Progression of primary disease should be reported on a response assessment eCRF in this FIH study. Events unequivocally related only to progression of primary disease do not need to be reported separately on the AE CRF page. Hospitalization to start new therapy for primary disease after confirmed progression/relapse does not meet reporting criteria for an AE or SAE.

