**Table 16. Ophthalmological evaluation**

Assessments a	Screen-ing b, c	Safety Run-In d		Cycle 1 (1 st combination cycle)	Cycle 2 & 3		Subse- quent Cycles	End of treatm ent i
		D15 e	D28 e		D1 f	D15 f		
Complete ophthalmic exam b	×	×	×	×	×	×	×	×
Visual field test g	×	×		×	×	×	×	×
SD-OCT h	×	×	×	×	×	×	×	×
Color fundus photography	×	×	×	×	×	×	×	×
Fundus autofluorescence	×	×		×	×	×	×	×
Fluorescein angiography	×			×	×	×		

- a. All evaluations are to be performed prior to administration of a next scheduled dose.
- b. Complete ophthalmic exam includes best corrected distance visual acuity utilizing Early Treatment Diabetic Retinopathy Study (ETDRS) scale, intraocular pressure measurement using Tono-Pen or Goldmann (the same modality should be used throughout the study), slit lamp exam (anterior and posterior segments), dilated fundus (using indirect ophthalmoscopy). Additional testing may be performed at discretion of the retina specialist. Applicable ophthalmologic assessment may be repeated at an unscheduled visit during the study if clinically indicated. An ophthalmic CRF is completed by the examining retina specialist at each visit.
- c. Performed within 14 days of initial APR-548 administration.
- d. Applies to the 28-day safety run-in period for APR-548 monotherapy and the 28-day safety run-in period for APR-548 in combination with azacitidine.
- e. A window of  $\pm 4$  days is allowable for this visit. This visit has to be completed prior to Cycle 1 Day 1 (1st combination cycle).
- f. A window of  $\pm 5$  days is allowable for this visit.
- g. An automated, threshold perimetry with Humphrey visual field analyzer using 30-2 testing protocol.
- h. Spectral domain optical coherence tomography of the macula and optic nerve, including ganglion cell complex analysis with study-specified and standard data acquisition algorithms utilized.
- i. Visit conducted at 28 days ( $\pm 14$  days) after study treatment discontinuation.

Please consult the A20-11202 study ophthalmic reference manual and ocular assessment worksheets for details. Ocular assessment worksheets are to be completed by retina specialist and submitted to the site for each visit.

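### AE collection and the TEAE period close 30 days after the last dose, but the end-of-treatment eye examination may come on Day 42 or later, so a late ocular event can miss the TEAE and SAE summaries

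*Combined protocol and SAP*

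**What the plan says.** Three places close the adverse-event window at the same point.

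- Section 8.5, on what is tabulated: "Data summaries will include only TEAEs, defined as events occurring at the first administration of APR-548 up to and including 30 days after last dose".
- Section 7.1.2.1, on what is collected: "The end of the AE and SAE reporting period is 30 days after last dose of study treatment, unless the subject has withdrawn consent". The same sentence also lets a new therapy for the underlying disease end the period sooner.
- Table 12, on the clinical safety assessment: "Starting at the time of study treatment initiation through 30 days after last dose".

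The last scheduled eye examination has a wider window. Table 16, footnote i: "Visit conducted at 28 days ( $\pm 14$ days) after study treatment discontinuation". Table 12, footnote x, repeats it: "A window of $\pm$ 14 days is allowable for End of Treatment ophthalmological evaluation".

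The documents do not agree on the date from which the end-of-treatment visit is counted. Both footnotes count from discontinuation. Section 4.1.1 puts the final follow-up visit 28 days after the last dose. Section 6.8, which includes the eye evaluation in the visit, says: "This visit should take place within 28 days of the last dose of study treatment". For a drug that is held and never restarted, Section 4.1.1 adds that "end of treatment is defined as the date when the study drug was first held".

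**The concern.** Eye toxicity is the risk that this protocol singles out. The dog NOAEL behind the exposure limits is described with reference to it, new or worsening retinopathy of any grade is a DLT (Section 5.1.3), and ocular events of Grade 2 or higher are events of special interest to be reported as SAEs.

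The end-of-treatment examination is there to look for this toxicity after dosing stops. In Cycle 4 and later, eye evaluations fall on Day 1 only, since Section 6.7.3 confines the Day 15 evaluation to Cycle 3, and Table 16 footnote a places each evaluation before the next dose. For a subject stopping in those cycles, the end-of-treatment examination may be the only scheduled look at the eye after the final course, unless a further Day 1 examination takes place first.

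An examination can therefore be fully compliant and still find an event that the AE rules neither require to be recorded nor allow into the tables. The affected result is the second primary endpoint in Section 8.3.1, the frequency of related TEAEs and SAEs. With cohorts of 3 to 6 and at most 46 subjects, one omitted retinal event would be visible in that frequency.

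**Working it through.** The plan gives no figure of its own to reproduce. The check is day arithmetic, followed by tracing where a late event would be recorded.

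**Inputs.** AE, SAE and TEAE cut-off: 30 days after the last dose (Sections 7.1.2.1 and 8.5, Table 12). Eye examination: 28 ±14 days from its anchor (Table 12 footnote x, Table 16 footnote i). Last dose of a combination cycle: azacitidine on cycle Day 7 of 28 (Section 4.1). The lag *g* between last dose and discontinuation is not given in the documents; it is an assumption, taken here as 0 to 22 days.

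**Step 1: examination counted from the last dose (no assumption needed).**
- Earliest day: 28 − 14 = 14. Latest day: 28 + 14 = 42.
- Permitted days: 42 − 14 + 1 = 29.
- Permitted days past the cut-off (Days 31-42): 42 − 30 = 12.
- Share of permitted days: 12/29 = 41%. The nominal Day 28 is inside the cut-off.

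**Step 2: examination counted from discontinuation, *g* days after the last dose.** The window becomes 14 + *g* to 42 + *g*, with nominal day 28 + *g*.

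| Assumed discontinuation (last dose on cycle Day 7) | *g* | Window, days after last dose | Nominal day |
|---|---|---|---|
| Day 7 | 0 | 14-42 | 28 |
| Day 8 | 1 | 15-43 | 29 |
| Day 15 | 8 | 22-50 | 36 |
| Day 22 | 15 | 29-57 | 43 |
| Day 29 (next cycle's Day 1) | 22 | 36-64 | 50 |

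The nominal examination passes the cut-off once 28 + *g* > 30, that is, for any lag of more than 2 days.

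**Step 3: a new ocular event with onset dated after Day 30.**
- Ophthalmic CRF: recorded, because one is completed at each visit (Table 16 footnote b).
- Summary of ophthalmologic findings: included. Section 8.5 lists these findings separately from AEs, and that sentence has no date limit.
- SAE report: made if the event is serious, or an ocular event of Grade 2 or higher (Section 5.1.3), and the investigator judges it related (Section 7.1.2.6).
- AE record for a non-serious Grade 1 event: not required, because the reporting period is over.
- TEAE and SAE summaries: excluded by the definition in Section 8.5, even when the event was reported as a late related SAE.

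**The case against.** Much of the case on the other side stands, and it rules out several stronger readings.

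- **A reader might infer that late eye toxicity vanishes from the safety results.** It does not. The finding is on the ophthalmic CRF and in the separate summary of eye findings. What is lost is its classification and count as a TEAE or SAE. A findings table does not replace that count, because it carries no attribution and does not feed the primary endpoint.
- **A reader might infer that a late Grade 1 retinal change is not captured at all.** It is captured as an examination finding; it simply need not become an AE record.
- **A reader might take 36-64 days as the usual case and conclude that every final examination is too late.** That range assumes discontinuation on Day 29, which no section states. At that visit an eye examination is already scheduled (Sections 6.6.1 and 6.7.1). With the ±5 days that Table 16 gives the Cycle 2 and 3 visits, it falls on Days 24-34, or 17-27 days after a Day 7 dose, inside the cut-off. Section 6.8 would keep the whole end-of-treatment visit within 28 days of the last dose.
- **A reader might infer that the loss is greatest after long toxicity holds.** Section 4.1.1 dates end of treatment back to the start of the hold, so the length of the hold does not move that date. The same section does foresee an end-of-treatment visit when the decision not to restart comes after the 28-day follow-up, so late visits can occur, but nothing shows where loss would concentrate.
- **Detection is not onset.** An event that began by Day 30 and was seen on Day 40 still meets the TEAE definition. But the documents give no rule for dating a change found only at examination, so its inclusion would rest on each site's judgement.
- **Dose decisions are unaffected.** DLTs use their own 28-day periods, and the Grade 3 ocular stopping criterion in Section 8.4 has no 30-day limit.

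**Conclusion.** The mismatch is real and needs no assumption: Days 31-42, 12 of the 29 permitted days, lie after AE collection and the TEAE period have closed, even when the examination is counted from the last dose. Counting from a later discontinuation date widens the gap; the range up to 36-64 days rests on an assumed lag of up to 22 days and is only an illustration. The documents do not allow an estimate of how many subjects would be affected, and the 41% must not be read as one.

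The consequence is limited but touches a primary endpoint. A new ocular event dated after Day 30 stays visible as an eye finding, and a related SAE is still reported, yet neither enters the TEAE and SAE summaries. The end-of-treatment anchors also contradict each other and must be reconciled whatever view is taken of the window. This is a cheap improvement to make, and it does not threaten dose escalation or the RP2D.

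**What to change.** For ocular events only, in Section 7.1.2.1, Table 12 and Section 8.5, end AE and SAE collection and the TEAE period at the later of (a) 30 days after the last dose of either drug and (b) completion of the end-of-treatment ophthalmological evaluation, whether or not new therapy has started. Any event found at that examination then belongs in the tables, and the missing onset-dating rule no longer decides the matter. Extending the window for all AEs would be broader than the problem.

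Separately, reconcile the date from which the end-of-treatment visit is counted across Section 4.1.1, Section 6.8, Table 12 footnote x and Table 16 footnote i.

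The cost is protocol wording and one date rule in the TEAE programming, with no added visit or procedure. The drawback is that a few late ocular events not due to study drug may enter the tables.
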